9.3 Vital Sign Data

Vital signs include body temperature, respiratory rate, heart rate and systolic/diastolic blood pressure at supine and/or standing positions. Potential clinically relevant vital sign abnormalities will be listed, the criteria for which are provided in Appendix 1. Incidences of clinically relevant vital signs abnormalities based on observations during scheduled visits and unscheduled post-baseline visits will be tabulated by treatment group. In addition, vital sign parameters and changes from baseline will be summarized using descriptive statistics by treatment and scheduled visit.

If vital sign assessments are repeated for the same trial visit, the last repeated values will be used for production of summary tables. This is accomplished by sorting subject data by visit date and visit time (if applicable) within the same trial visit.

9.4 Clinical Laboratory Data

Clinical laboratory tests include serum chemistry, hematology, and urinalyses analyses. Potentially clinically relevant laboratory test abnormalities will be listed by subject and by test. Criteria for potentially clinically relevant laboratory test abnormalities are provided in Appendix 2. Subjects with aspartate aminotransferase (AST) or alanine aminotransferase (ALT) \geq 3 × upper limit of normal value and total bilirubin \geq 2 × upper limit of normal value or baseline will be listed.

The incidences of potentially clinically relevant laboratory tests abnormalities based on observations during scheduled and unscheduled post-baseline visits will be tabulated by treatment group. Summary statistics for clinical laboratory measurements and changes from baseline will be presented by treatment group and scheduled visit. Change from baseline in fasting triglycerides and total cholesterol at Week 8/ET will be analyzed using ANCOVA including treatment group as fixed factor and baseline as covariate.

If laboratory tests assessments are repeated for the same mapped trial visit, the last repeated values will be used for summary tables. This is accomplished by sorting subject data by visit date and visit time (if applicable) within the same trial visit. If the lab data are recorded as ranges (ie, including < or > limit of quantification), these data are not

included in the calculations for changes from baseline but included in the calculations for incidences.

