Appendix 1 Criteria for Identifying Vital Signs and Weight of Potential Clinical Relevance

Variable	Criterion Value ^a	Change Relative to Baseline ^a
Heart Rate ^b	> 100 bpm < 50 bpm	≥ 10 bpm increase ≥ 10 bpm decrease
Systolic Blood Pressure ^b	≥ 140 mmHg < 90 mmHg	≥ 20 mmHg increase ≥ 20 mmHg decrease
Diastolic Blood Pressure ^b	≥ 90 mmHg < 60 mmHg	≥ 10 mmHg increase ≥ 10 mmHg decrease
Orthostatic Hypotension	≥ 30 mmHg decrease in systolic blood pressure or a ≥ 20 mmHg in diastolic blood pressure after at least 3 minutes of standing compared to the previous supine blood pressure.	Not Applicable (baseline status not considered)
Orthostatic Tachycardia	≥ 25 bpm increase in heart rate from supine to standing	Not Applicable (baseline status not considered)
Weight	-	≥ 7% increase ≥ 7% decrease

a In order to be identified as potentially clinically relevant, an on-treatment value must meet the "Criterion Value" and also represent a change from the subject's baseline value of at least the magnitude shown in the "Change Relative to Baseline" column.

b As defined in "Supplementary Suggestions for Preparing an Integrated Summary of Safety Information in an Original NDA Submission and for Organizing Information in Periodic Safety Updates," FDA Division of Neuropharmacological Drug Products draft (2/27/87).

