Appendix 2 Criteria for Identifying Laboratory Values of Potential Clinical Relevance

Laboratory Tests Criteria			
Chemistry			
AST (SGOT) $\geq 3 \times \text{upper limit of normal (ULN)}$			
ALT (SGPT)	$\geq 3 \times ULN$		
Alkaline phosphatase	$\geq 3 \times ULN$		
BUN	\geq 30 mg/dL		
Creatinine	$\geq 2.0 \text{ mg/dL}$		
Uric Acid			
Men	$\geq 10.5 \text{ mg/dL}$		
Women	$\geq 8.5 \text{ mg/dL}$		
Bilirubin (total)	$\geq 2.0 \text{ mg/dL}$		
Creatine Phosphokinase (CPK)	> 3 x ULN		
Hematology			
Hematocrit			
Male	\leq 37 % and decrease of \geq 3 percentage points from Baseline		
Female	\leq 32 % and decrease of \geq 3 percentage points from Baseline		
Hemoglobin			
Men	$\leq 11.5 \text{ g/dL}$		
Women	$\leq 9.5 \text{ g/dL}$		
White blood count	$\leq 2,800/ \text{ mm}^3 \text{ or } \geq 16,000/ \text{ mm}^3$		
Eosinophils	≥ 10%		
Neutrophils	≤ 15%		
Absolute neutrophil count	\leq 1,500/ mm ³		
Platelet count	\leq 75,000/ mm ³ or \geq 700,000/ mm ³		
Urinalysis			
Protein	Increase of ≥ 2 units		
Glucose	Increase of ≥ 2 units		
Additional Criteria			
Chloride	\leq 90 mEq/L or \geq 118 mEq/L		
Potassium	$\leq 2.5 \text{ mEq/L or} \geq 6.5 \text{ mEq/L}$		
Sodium	$\leq 126 \text{ mEq/L or} \geq 156 \text{ mEq/L}$		
Calcium	$\leq 8.2 \text{ mg/dL or} \geq 12 \text{ mg/dL}$		
Glucose			
Fasting	$\geq 100 \text{ mg/dL}$		
Non-Fasting	$\geq 200 \text{ mg/dL}$		
Total Cholesterol, Fasting	$\geq 240 \text{ mg/dL}$		
LDL Cholesterol, Fasting	$\geq 160 \text{ mg/dL}$		
HDL Cholesterol, Fasting			
Male	< 40 mg/dL		
Female	< 50 mg/dL		
Triglycerides, Fasting	≥ 150 mg/dL		

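### Laboratory abnormality incidence (SAP 9.4, CT-10.3) sets no condition on baseline status, so in the unscreened threshold rows, chiefly fasting glucose and lipids, pre-existing and new abnormalities are counted together

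*SAP*

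**What the plan says.** SAP 9.4 tabulates by treatment group "The incidences of potentially clinically relevant laboratory tests abnormalities based on observations during scheduled and unscheduled post-baseline visits". It adds that "Criteria for potentially clinically relevant laboratory test abnormalities are provided in Appendix 2". It sets no condition on the baseline value and names no denominator. The planned table, CT-10.3 in SAP Appendix 4, adds neither. No laboratory shift or new-onset table is listed there.

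The rows of Appendix 2 are of two kinds:

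- **Referred to baseline or to change.** Hematocrit needs a low value and a fall of at least 3 "percentage points from Baseline". Urine protein and urine glucose need "Increase of ≥ 2 units".
- **Bare thresholds.** Nearly everything else. For example, "Triglycerides, Fasting" is flagged at 150 mg/dL or more, fasting glucose at 100 or more, and fasting total cholesterol at 240 or more.

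Other safety sections of the SAP do refer to baseline. Footnote a of Appendix 1 (vital signs) begins "In order to be identified as potentially clinically relevant, an on-treatment value must meet the" tabled limit, and goes on to require a change of stated size from baseline as well. Appendix 3 (ECG) carries the same footnote. Table 9.6-1 counts a QT or QTc threshold only when it was not already exceeded at baseline.

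**The concern.** A by-arm incidence of abnormal laboratory values is usually read as what appeared on treatment. If subjects who were abnormal at entry and remained so are included, each arm's rate is a mixture of entry status and on-treatment change. The share due to entry status says nothing about the drug. It raises both rates, usually weakens the contrast, and carries any chance imbalance at baseline into the table as an apparent difference.

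The entry criteria leave room for this. Exclusion criterion 17 in Protocol 5.2.2 has no limit on lipids, glucose, uric acid or CPK. HbA1c is exclusionary only from 7%, and BMI may reach 45 kg/m². Neutrophils are exclusionary at 1000/mm³ or below but flagged at 1500 or below. Hemoglobin is exclusionary at 9 g/dL or below but flagged at 11.5 or below in men and 9.5 or below in women. Total cholesterol and triglycerides are also named among the safety endpoints in the protocol's objectives table.

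**Working it through.** **The plan's own figure.** The documents give no expected laboratory incidence, so there is nothing to reproduce on this point. The only input taken from them is 42 randomized subjects per arm (SAP 3.3). Prevalence, onset and persistence below are assumptions.

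**Step 1. Which rows are exposed?** Entry limit (Protocol 5.2.2, criterion 17) against flag (SAP Appendix 2):

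| Test | Excluded at entry | Flag | Exposed? |
|---|---|---|---|
| AST, ALT | > 2 × ULN | ≥ 3 × ULN | largely no |
| Creatinine | ≥ 2 mg/dL | ≥ 2.0 mg/dL | largely no |
| Platelets (low) | ≤ 75,000/mm³ | ≤ 75,000/mm³ | largely no |
| Hematocrit, urine protein, urine glucose | none | includes a change | no |
| Neutrophils | ≤ 1000/mm³ | ≤ 1500/mm³ | yes, narrow window |
| Hemoglobin | ≤ 9 g/dL | ≤ 11.5 (men), ≤ 9.5 (women) | yes, narrow window |
| Fasting glucose, total cholesterol, triglycerides | none (HbA1c ≥ 7% only) | ≥ 100, ≥ 240, ≥ 150 mg/dL | yes |
| Uric acid, CPK | none | threshold only | yes |

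**Step 2. Expected size with equal persistence.** Let b be the proportion abnormal at baseline, s the proportion of those still abnormal afterwards, and p the new-onset rate among subjects normal at baseline.

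- Rate when every post-baseline abnormality counts = b·s + (1 − b)·p.
- New-onset rate among those at risk = p.
- With the same b and s in both arms, the risk difference is (1 − b)(p₁ − p₀).

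Take p₁ = 15% and p₀ = 5% (difference 10 points, ratio 3.0), with s = 100%:

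| b | Tabulated rates | Difference (points) | Ratio | At risk per arm, 42(1 − b) |
|---|---|---|---|---|
| 0 | 15.0% vs 5.0% | 10.0 | 3.00 | 42 |
| 10% | 23.5% vs 14.5% | 9.0 | 1.62 | 38 |
| 20% | 32.0% vs 24.0% | 8.0 | 1.33 | 34 |
| 30% | 40.5% vs 33.5% | 7.0 | 1.21 | 29 |
| 50% | 57.5% vs 52.5% | 5.0 | 1.10 | 21 |

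At b = 30%, for example, 0.30 + 0.70 × 0.15 = 0.405 and 0.30 + 0.70 × 0.05 = 0.335. With s = 80% at b = 30% the rates are 34.5% and 27.5%: the same 7 points, ratio 1.25.

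**Step 3. Unequal persistence.** Keep p at 15% and 5%, and take b = 40%.

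- s = 95% on drug and 80% on placebo: 0.38 + 0.09 = 47% vs 0.32 + 0.03 = 35%. The difference is 12 points, larger than the 10 points for new onset.
- The reverse: 0.32 + 0.09 = 41% vs 0.38 + 0.03 = 41%. The difference vanishes.

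So shrinkage is the expected result only when persistence is similar across arms.

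**Step 4. Chance imbalance.** For two arms of 42 with the same true b, the binomial probability that they differ by 5 or more baseline-abnormal subjects is about 0.10 at b = 10%, 0.22 at b = 20% and 0.28 at b = 30%. Five subjects are 5/42, or about 12 points of incidence if they stay abnormal.

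**The case against.** **The SAP is silent and states no rule on these subjects.** A reader might infer that it orders subjects abnormal at baseline to be counted. It does not; it says only which visits supply the observations. But a threshold applied to post-baseline values with no further condition gives that count, so the point stands as a consequence of the text as written.

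**Not all tests are affected.** This is right. Three rows already require a change, and four tests are largely screened out at entry (Step 1). The neutrophil and hemoglobin windows are narrow, and nothing in the documents suggests that many subjects fall in them. If b is near 0 in a row, nothing is lost there.

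**The contrast with other sections is imperfect.** Appendix 1 expressly sets baseline aside for the two orthostatic rows, and the QTc row of Appendix 3 shows no change value. The two-part vital-sign rule is also not a new-onset rule: a subject above the limit at baseline who rises far enough is still flagged. What stands is that most vital-sign and ECG criteria refer to baseline in some way, and most laboratory rows do not.

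**A drug effect would still show elsewhere.** A reader might infer that it would be hidden. It would not: SAP 9.4 plans change-from-baseline summaries, listings by subject and by test, and a baseline-adjusted ANCOVA for triglycerides and total cholesterol. This weakens the point but does not remove it. The ANCOVA covers two analytes, and means do not show how many subjects newly crossed a limit.

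**The table is descriptive.** No test or error rate rests on it. In the illustration, a formal test of the new-onset contrast would have power of only about 0.30 at b = 10% and 0.25 at b = 30%. This keeps the importance low to moderate.

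**Conclusion.** The point holds for the absolute-threshold rows that entry criteria do not screen out: chiefly fasting glucose, total cholesterol and triglycerides, and to a lesser or unknown extent uric acid, CPK, neutrophils and hemoglobin. In these rows the count as written mixes persistence of an entry abnormality with onset on treatment.

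The factor (1 − b) follows by arithmetic if baseline prevalence and persistence are alike in the arms. The actual shrinkage is unknown, because the documents give no prevalence, onset or persistence. It is tempting to conclude that the metabolic rows will mainly show who was abnormal at entry, or that the contrast must be diluted. Neither is supported: the first needs a prevalence that is not given, and Step 3 shows that the second can fail in either direction.

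This is a low-to-moderate improvement to safety reporting. It has no bearing on the efficacy conclusions or on type I error.

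**What to change.** Keep the present CT-10.3 count and the listings, and add two things to SAP 9.4 and the table list:

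1. **New-onset incidence by arm in CT-10.3.** Numerator: subjects who meet the criterion at any scheduled or unscheduled post-baseline visit and did not meet it at baseline. Denominator: subjects with a baseline value that does not meet the criterion and at least one post-baseline value. Print the denominator in each row.
2. **A shift table** from baseline category to worst post-baseline category. Worsening in a subject already abnormal at baseline then stays visible; replacing the present count with new onset alone would drop it from the tables.

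No new data are needed. SAP 5.1 defines baseline as the last value before first dose, and the schedule has fasting laboratory tests at baseline, Week 4 and Week 8/ET.

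The cost is SAP wording and some programming. At-risk denominators in the metabolic rows will be smaller, and not always slightly: 29 of 42 per arm if 30% are abnormal at baseline, and 21 if 50% are. Those rates will be less precise, which is a further reason to show both counts.

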9.4.1.6 Other Efficacy Endpoint Analysis

Not applicable.

9.4.2 **Safety Analysis**

9.4.2.1 **Adverse Events**

All AEs will be coded by system organ class and MedDRA preferred term. The incidence of the following events will be summarized by treatment group:

- **TEAEs**
- TEAEs by severity
- TEAEs potentially causally related to the IMP
- TEAEs with an outcome of death
- Serious TEAEs
- TEAEs leading to discontinuation of the IMP

9.4.2.2 **Clinical Laboratory Data**

Summary statistics for changes from baseline in the routine clinical laboratory measurements will be provided. In addition, potentially clinically significant laboratory

results will be identified using criteria prospectively defined in the SAP and will be summarized. Change from baseline in fasting triglycerides and total cholesterol at Week 8/ET will be analyzed using analysis of covariance including treatment group, trial center as fixed factors and baseline as covariate.

9.4.2.3 **Physical Examination and Vital Signs Data**

By-subject listings will be provided for physical examination findings. Summary statistics for changes from baseline in vital signs will be provided. Potentially clinically significant results in vital signs and body weight will also be summarized. In addition, change from baseline in body weight and percentage of change from baseline in body weight will be analyzed using MMRM.

9.4.2.4 **Electrocardiogram Data**

Summary statistics for change from baseline and incidence of clinically significant changes will be calculated for ECG parameters.

For the analysis of OT and OTc, data from 3 consecutive complexes (representing 3 consecutive heart beats) will be measured to determine average values. The following QT corrections will be used for reporting purposes in the clinical study report:

- QTcF is the length of the QT interval corrected for heart rate by the Fredericia formula: $OTcF = OT / (RR)^{0.33}$
- QTcN is the length of the QT interval corrected for heart rate by the FDA Neuropharm Division formula: $QTcN = QT / (RR)^{0.37}$

In addition, potentially clinically significant ECG results will be identified using criteria prospectively defined in the SAP and will be summarized.

9.4.2.5 **Other Safety Data**

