- CT-9.4 Listing of Treatment-Emergent Adverse Events of Special Interests related to Rash
- CT-9.5 Listing of Treatment-Emergent Adverse Events related to Abuse
- CT-9.6 Listing of Treatment-Emergent Adverse Events involving Medication Handling Irregularities
- CT-10.1 Criteria for Laboratory Test Values with Potential Clinical Relevance
- CT-10.2.1 Listing of Laboratory Test Values with Potential Clinical Relevance by Subject (Safety Analysis Set)
- CT-10.2.2 Listing of Laboratory Test Values with Potential Clinical Relevance by Test (Safety Analysis Set)
- CT-10.3 Incidence of Laboratory Test Values with Potential Clinical Relevance (Safety Analysis Set)
- CT-10.4.1.1 Summary of Change from Baseline in Clinical Laboratory Test Results Serum Chemistry (Safety Analysis Set)
- CT-10.4.1.2 Summary of Change from Baseline in Clinical Laboratory Test Results Lipid Parameters ANCOVA (Safety Analysis Set)
- CT-10.4.2 Summary of Change from Baseline in Clinical Laboratory Test Results Hematology (Safety Analysis Set)
- CT-10.4.3 Summary of Change from Baseline in Clinical Laboratory Test Results Urinalysis (Safety Analysis Set)
- CT-10.5.1 Incidence of Potentially Liver Injury Related Laboratory Test Abnormalities (Safety Analysis Set)
- CT-10.5.2 Listing of Potentially Liver Injury Related Laboratory Test Abnormalities (Safety Analysis Set)
- CT-11.1 Criteria for Potentially Clinically Relevant Abnormalities in Vital Signs
- CT-11.2 Listing of Potentially Clinically Relevant Abnormalities in Vital Signs (Safety Analysis Set)
- CT-11.3 Incidence of Potentially Clinically Relevant Abnormalities in Vital Signs (Safety Analysis Set)
- CT-11.4 Summary of Change from Baseline in Vital Signs (Safety Analysis Set)
- CT-12.1 Criteria for Potentially Clinically Relevant Abnormalities in ECG Evaluations
- CT-12.2 Listing of Potentially Clinically Relevant Abnormalities in ECG Evaluations (Safety Analysis Set)
- CT-12.3 Incidence of Potentially Clinically Relevant Changes in ECG Evaluations (Safety Analysis Set)
- CT-12.4 Mean Change from Baseline in Electrocardiogram Results (Safety Analysis Set)

- CT-12.5 Incidence of Categorical Changes in QT/QTc (Safety Analysis Set)
- CT-13.1.1 Summary of Change from Baseline in Body Weight by Mapped Week MMRM (Safety Analysis Set)
- CT-13.1.2 Summary of Change from Baseline in Body Weight by Mapped Week ANCOVA (Safety Analysis Set)

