#### AE-1 Adverse Events

LAB-1 Laboratory Test Results: Serum Chemistry

LAB-2 Laboratory Test Results: Hematology

LAB-3 Laboratory Test Results: Urinalysis

LAB-4 Laboratory Test Results: Urine Drug Screen

LAB-5 Laboratory Test Results: Urine Pregnancy Test

LAB-6 Laboratory Test Results: Other Laboratory Tests

STAT-1.1.1 SAS Output for Change from Baseline in Binge Eating Days per Week - MMRM (Efficacy Analysis Set)

- STAT-1.1.2 SAS Output for Change from Baseline in Binge Eating Days per Week ANCOVA (Efficacy Analysis Set)
- STAT-1.2.1 Residual Analysis of MMRM for Change from Baseline in Binge Eating Days per Week Shapiro-Wilk Test (Efficacy Analysis Set)
- STAT-1.2.2 SAS Output for Residual by Week from MMRM for Change from Baseline in Binge Eating Days per Week (Efficacy Analysis Set)
- STAT-2.1 SAS Output for Change from Baseline in Clinical Global Impression Severity Score MMRM (Efficacy Analysis Set)
- STAT-2.2 SAS Output for Change from Baseline in Clinical Global Impression Severity Score ANCOVA (Efficacy Analysis Set)
- STAT-3 Estimated Effect Size for Efficacy Endpoints by End of Week 8
- STAT-4.1.1 Summary of Change from Baseline in Binge Eating Days per Week by Gender MMRM (Efficacy Analysis Set)
- STAT-4.1.2 Summary of Change from Baseline in Binge Eating Days per Week by Race MMRM (Efficacy Analysis Set)
- STAT-4.1.3 Summary of Change from Baseline in Binge Eating Days per Week by Age MMRM (Efficacy Analysis Set)
- CF-1.1 Plot for Change from Baseline in Binge Eating Days per Week
- CF-1.2 Forest plot for Sensitivity Analysis of Change from Baseline in Binge Eating Days per Week
- CF-2.1 Plot for Change from Baseline in Clinical Global Impression Severity Score
- CF-2.2 Forest Plot for Sensitivity Analysis of Change from Baseline in Clinical Global Impression Severity Score
- CF-3 Incidence of Treatment-Emergent Adverse Events of at Least 5% in Any Centanafadine Group and Greater Than Placebo
- CF-4.1 Mean of Change from Baseline in Binge Eating Days per Week by Dropout Cohort OC: Centanafadine 400mg
- CF-4.2 Mean of Change from Baseline in Binge Eating Days per Week by Dropout Cohort OC: Centanafadine 200mg
- CF-4.3 Mean of Change from Baseline in Binge Eating Days per Week by Dropout Cohort OC: Placebo

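### Laboratory results reported above a quantification limit are left out of every change-from-baseline analysis, including the lipid ANCOVA, which would shrink a drug-related rise by an unknown and possibly zero amount

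*SAP*

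**What the plan says.** SAP 9.4 (Clinical Laboratory Data) deals with results that the laboratory reports only as beyond a limit. The rule begins "If the lab data are recorded as ranges (ie, including < or > limit of quantification), these data are not". It leaves such results out of every change-from-baseline calculation and keeps them when incidences are counted.

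The same section sets out the analyses that this reaches:

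- Descriptive summaries: "Summary statistics for clinical laboratory measurements and changes from baseline will be presented by treatment group and scheduled visit".
- The lipid model, which takes change from baseline as its outcome. Protocol 9.4.2.2 plans it too: "Change from baseline in fasting triglycerides and total cholesterol at Week 8/ET will be analyzed using analysis of covariance". Appendix 4 gives it its own table: "CT-10.4.1.2 Summary of Change from Baseline in Clinical Laboratory Test Results Lipid Parameters ANCOVA (Safety Analysis Set)".

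Neither document exempts the lipid model. Protocol 9.4.2.2 does not mention results beyond a limit, and SAP section 15 lists only the removal of trial center from this ANCOVA. Protocol Table 3-1 names change from baseline in total cholesterol and triglycerides among the safety endpoints.

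The results are kept elsewhere. The incidence table is "CT-10.3 Incidence of Laboratory Test Values with Potential Clinical Relevance (Safety Analysis Set)", and Appendix 5 lists individual results, starting with "LAB-1 Laboratory Test Results: Serum Chemistry".

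**The concern.** A result reported as `>` a limit is not missing. It says that the value is at least the limit. When it occurs after baseline, the rule removes the pair because of the outcome itself, and what it removes is the top of the distribution. With no drug effect this cancels between arms. If the drug raises the analyte, more pairs are expected to go from the drug arms than from placebo, and the remaining means understate the rise. Here that would make a safety estimate look smaller than it is.

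A reader could not tell from the planned tables whether this had happened. No title in Appendix 4 promises a count of excluded results by arm, although titles are not table shells and the listings plausibly show the individual values.

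The point covers `>` results only. Nothing is claimed about `<` results.

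**Working it through.** The documents state no figure for this rule, so there is none to reproduce. They also give no quantification limits, crossing rates or expected lipid changes. Every distributional input below is an assumption. The only figure taken from the plan is 42 randomized subjects per arm.

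**1. Direction.** Let the post-baseline value be Y = mu + e, and drop values above L. Put t = L - mu, and let f and F be the density and distribution function of e. Then

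d/dmu E[Y | Y < L] = 1 - (f(t)/F(t)) × (t - E[e | e < t]).

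The subtracted term cannot be negative, so the slope is at most 1: a uniform rise of one unit moves the retained mean by one unit or less. Example with standard normal e, L = 2 and a rise of 0.5, looking at the post-baseline value alone:

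- Placebo: 0 - 0.0540/0.9772 = -0.055
- Drug: 0.5 - 0.1295/0.9332 = 0.361
- Retained difference: 0.361 + 0.055 = 0.416, against a true 0.500

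**2. Size in expectation.** Assumed model: baseline = exp(0.6z) and post = k × exp(0.6(0.6z + 0.8e)), with k = 1.0 on placebo and 1.3 on drug. That is a log-SD of 0.6, a correlation of 0.6 on the log scale and a 30% rise. The true difference is 0.3 × exp(0.6²/2) = 0.3 × 1.197 = 0.359 untreated medians. Simulation used 4,000,000 subjects per arm and dropped a pair if either visit exceeded the limit.

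| Limit (percentile of untreated values) | Current rule: drop | Drop, ANCOVA | Set to the limit |
|---|---|---|---|
| 95th | 0.242 | 0.227 | 0.284 |
| 99th | 0.306 | 0.298 | 0.334 |
| 99.9th | 0.345 | 0.343 | 0.354 |
| 99.99th | 0.356 | 0.355 | 0.358 |

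Shortfall at the 99th: (0.359 - 0.306)/0.359 = 15% dropping, and (0.359 - 0.334)/0.359 = 7% setting to the limit. At the 99.9th the figures are 4% and 1%. At the 99.99th both are under 1%. Pairs dropped, drug against placebo, are 3.6% against 1.8% at the 99th and 0.5% against 0.2% at the 99.9th.

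**3. Dependence on the model.** With a normal analyte (rise 0.5 SD, correlation 0.6, true difference 0.500), a limit at the 99th percentile gives 0.478 dropping and 0.490 setting to the limit, so 4% and 2% low. The direction is the same and the size smaller.

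**4. One trial of 42 per arm** (log-normal model, limit at the 99th, 200,000 trials). No pair is dropped in 10% of trials. In the rest, the estimate after dropping lies below the full-data estimate in 72% and above it in 28%. Setting to the limit is closer to the full-data estimate in 87% (mean distance 0.045 against 0.094). With the limit at the 99.9th, no pair is dropped in 76% of trials.

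**5. Precision.** At the 99th percentile the mean standard error is 0.175 with full data, 0.150 dropping and 0.158 setting to the limit. Rejection rates are 53%, 53% and 56%. Root mean squared error is 0.159 dropping and 0.161 setting to the limit; at the 95th percentile it is 0.173 and 0.152.

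**The case against.** The strongest reply is that no loss is shown in this trial. The limits, the spread and the 30% rise are all assumed. Modern assay ranges may be wide enough that no result is ever reported as `>`. That stands, and it is why the size is left open.

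Second, the proposed change does not lower total error when few values cross: 0.159 against 0.161 at the 99th percentile. That also stands, but it carries less weight than it seems to. In the same model, complete uncensored data have a root mean squared error of 0.178, so dropping beats even perfect measurement only because it trims a heavy tail. With a log-SD of 0.2 and a 30% rise, setting to the limit does better (0.049 against 0.061). The gain claimed is less bias, and setting to the limit had less bias in every case checked: log-SD 0.2 and 0.6, rises of 10% and 30%, limits at the 95th, 99th and 99.9th percentiles.

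Third, a reader might infer that the plan hides a lipid signal. The documents do not support that. The same sentence keeps these results in the incidences. Appendix 2 has fasting thresholds for both lipids (the row "Triglycerides, Fasting" at 150 mg/dL, and total cholesterol at 240 mg/dL), so a `>` result counts there whenever its limit is at or above the threshold. What the incidence table cannot supply is the mean difference.

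Fourth, a reader might take attenuation to be a general law. It is not. In a contrived case where only subjects with below-average baseline respond, the ANCOVA difference rose slightly, from 0.249 to between 0.254 and 0.258. The claim needs a roughly uniform or proportional rise.

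**Conclusion.** The point holds as a minor one. SAP 9.4 removes `>` results from all laboratory changes from baseline, the lipid ANCOVA is not exempt, and for a post-baseline result the removal depends on the outcome. If a drug raises an analyte roughly uniformly or proportionally and some values pass the limit, the estimated mean difference is too small in expectation. A single trial of this size can move either way.

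The size is unknown. It is zero if no result is reported as `>`, and negligible unless about 1% or more of values cross. The 15% figure belongs to one assumed log-normal model with the limit at the 99th percentile and should not be read as an estimate for this trial.

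A reader might also infer that the test for a lipid rise loses power. The calculations do not show this: the standard error falls with the estimate, and the rejection rate is 53% either way. What suffers is the size of the estimate. The efficacy analyses, the type I error plan and the sample size are untouched. This is a worthwhile tidy-up and does not threaten the trial's conclusions.

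**What to change.** Amend SAP 9.4 before unblinding, along these lines:

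*For changes from baseline and the lipid ANCOVA, a result reported as `>` a limit of quantification is set to that limit. All other results recorded as ranges, including `<` a limit, remain excluded from changes from baseline. The number of substituted and excluded results is footnoted by test and treatment group. Incidence calculations are unchanged.*

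This keeps a rule for every kind of range result and does not extend substitution to summaries that the present exclusion does not cover. The footnote is useful by itself, because it shows whether the issue arose at all.

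The cost is a short text change, one programming step and a footnote. There are three downsides. The substituted value still understates the extreme. The change is 0 when both visits exceed the same limit (0.4% of drug-arm pairs in the log-normal model with a 99th-percentile limit). Total error is about the same when few values cross.
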